6.3 MEASURES TO MINIMIZE BIAS: RANDOMIZATION AND BLINDING

All participants will be centrally assigned to randomized IMP using an interactive response technology (IRT). The Investigator will be questioned during the interactive voice response system (IVRS) phone call/interactive web response system (IWRS) web module if he/she wishes to enroll the participant in the study. Before the study is initiated, the telephone number and call-in directions for the IVRS and/or the log in information and directions for the IWRS will be provided to each site.

At the screening visit (Visit 1), the Investigator or designee will contact the IRT system to receive the participant number. If a participant who had previously failed screening is approached for rescreening, a new ICF must be signed. In such case, a new participant number will be assigned by IRT.

Methods of assigning participants to treatment group

The randomized intervention kit number list is generated centrally by Sanofi and IMPs (dupilumab 300 mg, dupilumab 200 mg, or their matching placebo) are packaged in accordance with this list. The randomization and intervention allocation are performed centrally by an IRT. The IRT generates the participant randomization list and allocates the intervention number and the corresponding intervention kits to the participants according to it.

Participants will be randomized in a 1:1 ratio treatment arm as described in the [Table 3](#).

Randomization will be stratified by age (adolescent versus adult) and within adult group by country and background H1-antihistamine regular/daily use (Yes/No) (see [Section 6.1.2](#) for additional background therapy details).

Number of participants using H1-antihistamine as needed prior to study entry should be at least █. At screening (Visit 1), the Investigator or designee will contact the IRT system to receive the participant number. If a participant who had previously failed screening is approached for re-screening, a new ICF must be signed. In such case, a new participant number will be assigned by IRT.

A randomized participant is defined as a participant who has been allocated to a randomized intervention regardless of whether the treatment was administered or not (ie. participant registered by the IRT). A participant cannot be randomized more than once in the study.

Study intervention will be dispensed at the study visits summarized in schedule of activities (SoA) ([Section 1.3](#)). Returned study intervention should not be re-dispensed to the participants.

Methods of blinding

Dupilumab 300 mg/200 mg and placebo matching dupilumab 300 mg/200 mg will be provided in identically matched 2 mL/1.14 mL pre-filled syringes that are visually indistinguishable for each dose. Syringes and boxes will be labeled with a treatment kit number. Whilst this study is double-blinded in terms of treatment with either dupilumab or placebo, it is not blinded to weight-based dose levels, due to the different volume size (2 mL versus 1.14 mL) of the dose level of

dupilumab (300 mg/matching placebo or 200 mg/matching placebo) that will be used for the different weight categories for adolescents.

Code breaking

The IRT will be programmed with blind-breaking instructions. In case of an emergency, the Investigator has the sole responsibility for determining if unblinding of a participant's intervention assignment is warranted (eg, in case of available antidote). Participant safety must always be the first consideration in making such a determination. If the Investigator decides that unblinding is warranted, he/she may, at his/her discretion, contact the Sponsor to discuss the situation prior to unblinding a participant's intervention assignment unless this could delay emergency treatment of the participant. If a participant's intervention assignment is unblinded, the Sponsor must be notified within 24 hours after breaking the blind. The date and reason that the blind was broken must be recorded in the source documentation and the electronic case report form (eCRF), as applicable.

If the code is broken, the participant must withdraw from IMP administration.

6.4 STUDY INTERVENTION COMPLIANCE

- The Investigator or his/her delegate must ensure that IMP is administered to each participant according to the labeling instructions.
- Investigational medicinal product accountability:
 - Investigational medicinal product units are returned by the participant at each visit. In case of DTP process, the intervention units can be returned by the carrier (if defined in the contract).
 - The Investigator or his/her delegate counts the number of remaining kits/pre-filled syringes and fills in the Intervention Log Form.
 - The Investigator or his/her delegate records the dosing information on the appropriate pages of the eCRF.
 - The monitor in charge of the study then checks the eCRF data by comparing them with the IMP which he/she has retrieved and intervention log forms/source documents.
 - A paper diary will be dispensed to the participants for indicating IMP administration at home.

When participants are dosed at the study center, they will receive study intervention directly from the Investigator or designee, under medical supervision. The date and time of each dose administered in the clinic will be recorded in the source documents and recorded in the eCRF. The dose of study intervention and study participant identification will be confirmed at the time of dosing by a member of the study center staff other than the person administering the study intervention.

When participants self-administer study intervention(s) at home, compliance with study intervention will be assessed at each visit. Compliance will be assessed by checking diary and

used/unused kits/pre-filled syringes during the study center visits and documented in the source documents and eCRF. Deviation(s) from the prescribed dosage regimen should be recorded in the eCRF.

A record of the number of kits/pre-filled syringes dispensed to and taken by each participant must be maintained and reconciled with study intervention and compliance records. Intervention start and stop dates, including dates for intervention delays and/or dose reductions will also be recorded in the eCRF.

6.5 CONCOMITANT THERAPY

Any medication or vaccine (including over-the-counter or prescription medicines, vitamins, and/or herbal supplements) that the participant is receiving at the time of enrollment or receives during the study must be recorded along with:

- Reason for use.
- Dates of administration including start and end dates.
- Dosage information including dose and frequency.

Non-sedating H1-antihistamines, at up to 4-fold the approved dose for CSU, are allowed as background medication and on demand as rescue medication. See [Section 6.1.2](#) and [Section 6.5.1](#) for details.

The concomitant use of the following therapies is prohibited during the entire study. Study treatment will need to be discontinued in participants receiving these treatments:

- Systemic immunosuppressants (immunosuppressive/immunomodulating drugs)
eg, systemic corticosteroids (oral or parenteral [intravenous, intramuscular, SC]), cyclosporine, mycophenolate-mofetil, interferon gamma, Janus kinase inhibitors, azathioprine, methotrexate, hydroxychloroquine, dapsone, sulfasalazine, colchicine, etc.

Note: a short course of OCS is allowed as rescue therapy (see [Section 6.5.1](#))

- Any cell-depleting agents including but not limited to rituximab
- Monoclonal antibodies (which are biological response modifiers) including anti-IgE therapy (omalizumab)
- Treatment with a live (attenuated) vaccine
- IVIG
- Plasmapheresis
- Other investigational drugs.

The concomitant use of following therapies is prohibited during the entire study but study treatment will not need to be discontinued in participants receiving these treatments in violation of the protocol:

- Topical corticosteroids
- Topical calcineurin inhibitors
- Topical and oral antihistamines (other than those allowed as background or rescue therapy)
- Routine doses of doxepin (daily or every other day during 5 or more consecutive days)
- LTRAs and H2 receptor antagonists, unless stable and taken for diseases other than chronic inducible ColdU
- Antifibrinolytic tranexamic acid and epsilon-aminocaproic acid
- Phototherapy, including tanning beds.

6.5.1 Rescue medicine

All participants will be allowed to take study-defined H1-antihistamine (see [Section 6.1.2](#)) as rescue therapy as long as they do not exceed 4-fold the approved dose for CSU during the screening, treatment, and follow-up periods. If symptoms are still uncontrolled after increase of H1-antihistamine to the maximum allowed dose, or if the participant is already on the 4-fold approved H1-antihistamine, participants can switch to another antihistamine up to 4-fold the approved dose for CSU or a short course of OCS is allowed during the treatment and follow-up periods. In order to ensure consistency, when possible, it is recommended to use OCS for 5 to 7 days with a starting dose of oral prednisone 40 mg (or clinically comparable OCS) followed by taper per the Investigator's judgment.

Due to an episodic nature of ColdU, it is recommended to prescribe rescue therapy for a short period of time (not more than 7 days).

The ice cube provocation test should be delayed if rescue therapy (H1-antihistamine or OCS) is taken within 5 days prior to the test. The ice cube provocation test can be done when the participant is back to prescreening H1-antihistamine dose or is off H1-antihistamine (or OCS) intake for at least 5 consecutive days to allow to have ice cube provocation test performed under the same background condition for each participant from screening visit (Visit 1) to EOS (Visit 5).

In case of systemic hypersensitivity reactions due to cold, the participants may require epinephrine treatment. EpiPen (or a local equivalent) will be provided to the participants at the beginning of the study, and the participants should be appropriately trained how and when to use it. EpiPen use should be in accordance with the locally approved product labeling.

For rescue medication in participants in Japan, please see Appendix 8 ([Section 10.8](#)).

The initial background therapy should remain unchanged throughout the study. Participants should continue their prescreening dose of initial H1-antihistamine once rescue treatment is no longer required or stop H1-antihistamine intake. The use of permitted rescue medications should be delayed in all participants, if possible, for at least 8 weeks following the initiation of the investigational treatment. The date and time of rescue medication administration as well as the name and dosage regimen of the rescue medication must be recorded.

For other information including safety precautions related to H1-antihistamine, OCS, and EpiPen (or a local equivalent), please refer to the locally approved product labeling.

6.6 DOSE MODIFICATION

No change in IMP dose is allowed.

6.7 INTERVENTION AFTER THE END OF THE STUDY

The Sponsor will not be responsible for intervention after the EOS Visit. Intervention after the EOS Visit will be at the discretion of the Investigator or treating physician.

7 DISCONTINUATION OF STUDY INTERVENTION AND PARTICIPANT DISCONTINUATION/WITHDRAWAL

7.1 DISCONTINUATION OF STUDY INTERVENTION

7.1.1 Definitive discontinuation

In rare instances, it may be necessary for a participant to permanently discontinue study intervention. If study intervention is permanently discontinued, the participant should complete the early treatment discontinuation visit with all assessments planned for the end of treatment (EOT) Visit. See the SoA ([Section 1.3](#)) for data to be collected at the time of discontinuation of study intervention.

The participants may withdraw from treatment with the IMP if he or she decides to do so, at any time and irrespective of the reason, or this may be the Investigator's decision. All efforts should be made to document the reason(s) for treatment discontinuation, and this should be documented in the eCRF.

Participants must be permanently withdrawn from the study treatment for the following reasons:

- At their own request or at the request of their legally authorized representative (legally authorized representative means an individual or judicial or other body authorized under applicable law to consent on behalf of a prospective participant to the patient's participation in the procedure(s) involved in the research).
- If, in the Investigator's opinion, continuation in the study would be detrimental to the participant's well-being.
- At the specific request of the Sponsor.
- In the event of a protocol deviation, at the discretion of the Investigator or the Sponsor.
- Any code broken requested by the Investigator will lead to permanent discontinuation of study intervention.
- Pregnancy.
- Anaphylactic reactions or systemic allergic reactions that are related to IMP and require treatment (see [Section 10.9](#)).
- Diagnosis of a malignancy during study, excluding carcinoma in situ of the cervix, or squamous or basal cell carcinoma of the skin.
- Any opportunistic infection or other infections whose nature or course may suggest an immunocompromised status (see [Section 10.11](#)).
- Serum alanine aminotransferase (ALT) $>3 \times$ Upper Limit of Normal (ULN) and total bilirubin $>2 \times$ ULN (see [Section 10.6](#)).
- Serum ALT $>5 \times$ ULN if baseline ALT $\leq 2 \times$ ULN or ALT $>8 \times$ ULN if baseline ALT $>2 \times$ ULN (see [Section 10.6](#)).

- If the participant develops a medical condition that requires use of prohibited medication (see [Section 6.5](#)).
- If the participant misses more than 2 consecutive doses of the IMP (see [Section 7.1.2](#)).
- Systemic hypersensitivity reaction including anaphylaxis related or suspected to be related to ice cube provocation test. In the participants who experienced such reaction no further ice cube provocation test should be done during the study.

See the SoA ([Section 1.3](#)) for data to be collected at the time of intervention discontinuation and follow-up and for any further evaluations that need to be completed.

Any abnormal laboratory value or ECG parameter will be immediately rechecked for confirmation within a reasonable timeframe as assessed by the Investigator before making a decision of definitive discontinuation of the IMP for the concerned participant.

If a clinically significant ECG finding is identified (including, but not limited to changes from baseline in QT interval corrected using [Bazett's formula {QTcB} or Fridericia's formula {QTcF}]) at screening, the Investigator or qualified designee will determine if the participant is eligible for the study. This review of the ECG printed at the time of collection must be documented. Any new clinically relevant finding should be reported as an AE.

Handling of participants after definitive intervention discontinuation

Participants will be followed-up according to the study procedures specified in this protocol up to the scheduled date of study completion, or up to recovery or stabilization of any AE to be followed-up as specified in this protocol, whichever comes last.

Participants who discontinue the study intervention prematurely (prior to completing the 24-week treatment period) will perform, as soon as possible, the early treatment discontinuation Visit with all assessments normally planned for the EOT visit (Visit 4), to assure a complete clinical assessment in close temporal proximity to the premature termination of study treatment is available.

In addition, and to allow assessment of participant outcomes over the stipulated study period, participants will be asked and encouraged to complete all remaining study treatment visits and participate in safety follow-up according to the visit schedule with a ± 3 day window. Under exceptional circumstances when a participant cannot come to the study center for a scheduled visit, a phone contact can be made. During the phone contact, at least information about AEs, concomitant medication and status of urticaria should be collected.

All cases of permanent intervention discontinuation must be recorded by the Investigator in the appropriate pages of eCRF when considered as confirmed.

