7.1.2 Temporary discontinuation

Temporary intervention discontinuation may be considered by the Investigator because of suspected AEs or disruption of the clinical trial due to regional or national emergency declared by

a governmental agency (Appendix 9 [[Section 10.9](#)]). For all temporary intervention discontinuations, duration should be recorded by the Investigator in the appropriate pages of the eCRF.

In addition, if patients become infected while receiving treatment with dupilumab and do not respond to antihelminthic treatment, treatment with dupilumab should be temporarily discontinued until infection resolves.

If the participant misses more than 2 consecutive doses, the participant will be permanently discontinued from the study treatment.

For all temporary intervention discontinuations, duration should be recorded by the Investigator in the appropriate pages of the eCRF.

7.1.2.1 *Rechallenge*

Reinitiation of intervention with the IMP will be done under close and appropriate clinical/and or laboratory monitoring once the Investigator will have considered according to his/her best medical judgment that the responsibility of the IMP(s) in the occurrence of the concerned adverse event was unlikely and if the selection criteria for the study are still met (refer to [Section 5.1](#) and [Section 5.2](#)).

For a regional or national emergency declared by a governmental agency, contingency measures are included in Appendix 9 ([Section 10.9](#)).

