8.3.1 Time period and frequency for collecting AE and SAE information

All AEs, serious or nonserious, will be collected from the signing of the ICF until the EOS Visit at the time points specified in the SoA ([Section 1.3](#)).

All SAEs and AESIs will be recorded and reported to the Sponsor or designee immediately and under no circumstance should this exceed 24 hours, as indicated in Appendix 3 ([Section 10.3](#)). The Investigator will submit any updated SAE/AESI data to the Sponsor within 24 hours of it being available.

Investigators are not obligated to actively seek AEs or SAEs after conclusion of study participation. However, if the Investigator learns of any SAE, including a death, at any time after a participant has been discharged from the study, and he/she considers the event to be reasonably related to the study intervention or study participation, the Investigator must promptly notify the Sponsor.

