Other screening tests	
• For women of childbearing potential: serum pregnancy test at screening visit (Visit 1) and urine pregnancy tests at baseline visit (Visit 2) and every 4 weeks during the study. A negative result must be obtained at Visit 1 and at Visit 2 prior to randomization. In case of positive urine test the study treatment will be withheld and a serum pregnancy test to confirm the pregnancy should be performed as soon as possible. Pregnancy testing should be done monthly, female participants will be supplied with dipsticks for months with no study center visits planned. For the urine pregnancy tests performed at home female participants will have to complete a pregnancy test diary. In female participants who discontinue the study intervention the pregnancy testing should continue for minimum of 12 weeks after the last dose of study intervention.• Hepatitis serologic testing at screening visit (Visit 1): hepatitis B surface antigen (HBs Ag), hepatitis B surface antibody (HBs Ab), hepatitis B core antibody (HBc Ab), and hepatitis C virus antibodies (HCV Ab). In case of results showing HBs Ag (negative) and HBc Ab (positive), an HBV DNA testing will be performed and should be confirmed negative prior to randomization. In case of results showing HCV Ab (positive), an HCV RNA testing will be performed and should be confirmed negative prior to randomization.• Human Immunodeficiency Virus (HIV) serologic testing at screening visit (Visit 1): HIV screen (Anti-HIV-1 and HIV-2 antibodies).• Tuberculosis test (to be performed locally if required). 
The results of each test must be entered into the eCRF.

Abbreviations: DNA = deoxyribonucleic acid; eCRF = electronic case report form; HBV = hepatitis B virus, IEC = Institutional Ethics Committee; IRB = Institutional Review Board; RNA = ribonucleic acid; SAE = serious adverse event; ULN = Upper Limit of Normal.

NOTES :

- a Details of liver chemistry stopping criteria with suggested actions and follow-up assessments related to liver monitoring are given in [Section 7.1](#) and [Section 10.6](#). All events which may indicate severe liver injury (possible Hy's Law, ALT or AST $>3 \times$ ULN and total bilirubin $>2 \times$ ULN) must be reported as an SAE.
- b Local urine testing will be standard for the protocol unless serum testing is required by local regulation or IRB/IEC.

Investigators must document their review of each laboratory safety report.

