10.6 APPENDIX 6: LIVER AND OTHER SAFETY: ACTIONS AND FOLLOW-UP ASSESSMENTS

INCREASE IN ALT

*If unable to retest in 72 hours, use original lab results to decide on further reporting/monitoring/discontinuation.

Note:

[figure not shown]
“Baseline” refers to ALT sampled at baseline visit; or if baseline value unavailable, to the latest ALT sampled before the baseline visit. The algorithm does not apply to the instances of increase in ALT during screening.

[figure not shown]
See [Section 10.3](#) for guidance on safety reporting.

[figure not shown]
Normalization is defined as \leq ULN or baseline value, if baseline value is $>$ ULN.

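### The mandatory liver stopping bullets in Protocol 7.1.1 name ALT only, while Appendix 2 counts ALT or AST as possible Hy's Law; adding AST to the combined bullet is a cheap, low-severity improvement

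*Protocol*

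**What the plan says.** Protocol 7.1.1 has two liver bullets in its must-withdraw list. The combined one reads "Serum alanine aminotransferase (ALT) $>3 \times$ Upper Limit of Normal (ULN) and total bilirubin $>2 \times$ ULN". The other concerns ALT alone: above 5 times ULN if baseline ALT is at most 2 times ULN, or above 8 times ULN if baseline is higher. Both refer to 10.6. The same list includes the Investigator's opinion that continuing would harm the participant, and "At the specific request of the Sponsor".

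A recheck comes before any definitive stop: "Any abnormal laboratory value or ECG parameter will be immediately rechecked for confirmation within a reasonable timeframe as assessed by the Investigator".

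Note a to Table 9 in Appendix 2 first sends the reader to 7.1 and 10.6 for the liver stopping criteria, then sets the reporting rule for possible Hy's Law: "ALT or AST $>3 \times$ ULN and total bilirubin $>2 \times$ ULN) must be reported as an SAE". Section 10.6 is headed "INCREASE IN ALT". Its flow chart is not shown. One visible note says: "If unable to retest in 72 hours, use original lab results to decide on further reporting/monitoring/discontinuation".

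**The concern.** Note a links the two rules. It names 7.1 and 10.6 as the source of the stopping criteria and, in the next sentence, describes possible severe liver injury by either transaminase. A reader who follows the pointer to 7.1.1 finds a rule that leaves out AST, without explanation. Two participants with the same SAE classification can then be treated differently: one must stop once the values are confirmed, while the other meets no liver bullet in that section.

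What is at stake is participant safety in a rare event. The trial has no data monitoring committee (synopsis) and no study committees (10.1.5), and later doses may be self-injected at home (6.1.1), so a written rule has some value here. The retest timing also differs in the visible text. The 72-hour fallback stands under the ALT heading in 10.6, while 7.1.1 leaves the timing of a recheck to the Investigator.

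**Working it through.** The plan gives no figure to reproduce. The check is one of logic, followed by a dose count.

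**Rules** (all values in multiples of ULN)
- A, 7.1.1 combined: ALT > 3 and bilirubin > 2.
- B, 7.1.1 ALT alone: ALT > 5 if baseline ALT ≤ 2, or ALT > 8 if baseline ALT > 2.
- H, Appendix 2 note a: (ALT > 3 or AST > 3) and bilirubin > 2.

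**Illustrative cases** (assumed values)
- ALT 2.5, AST 4, bilirubin 2.5: A false, B false, H true.
- ALT 3.0, AST 3.1, bilirubin 2.1: A false, B false, H true.
- ALT 3.5, AST 4, bilirubin 2.5: A true, B false, H true.

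The gap is every case with AST > 3, ALT ≤ 3 and bilirubin > 2. A fails because ALT is not above 3, and B fails because it needs ALT above 5 or 8. If A becomes (ALT or AST) > 3 and bilirubin > 2, it is identical to H and the gap closes.

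**Doses that a mandatory stop could affect.** Dosing is every 2 weeks from Week 0 to Week 22, so 22/2 + 1 = 12 occasions. Chemistry is scheduled at screening and Weeks 0, 12, 24 and 36 (Schedule of Activities), so Week 12 is the only scheduled sample between the first and last dose. I assume that the Week 12 dose is given before the result is known.
- Confirmed before the Week 14 dose: Weeks 14, 16, 18, 20 and 22 remain, 5/12 = 42%.
- Confirmed after the Week 14 dose: Weeks 16, 18, 20 and 22 remain, 4/12 = 33%.
- First seen at Week 24 or 36: 0.
- Unscheduled test at Week 3, confirmed before the Week 4 dose: Weeks 4 to 22 remain, 10/12 = 83%. Appendix 2 allows additional tests at any time.

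These are scenarios, not bounds. Each falls to zero if the Investigator or Sponsor would have stopped dosing anyway.

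**The case against.** The strongest reply is that a reporting rule and a stopping rule do different jobs, and the first may properly be wider. ALT-only wording is the more common form in the two documents: it also appears in the AESI definition (8.3.7), the SAE examples (10.3.2), the 10.6 heading and SAP Table 7. In the drug-induced liver injury list of SAP 4.7.3.1, only the first of three items names AST. The convention may be deliberate. This stands, and it is why the point is not an error.

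A reader might infer that an AST-driven case escapes oversight. The documents do not support that. It is an SAE, and for those 8.3.1 says: "All SAEs and AESIs will be recorded and reported to the Sponsor or designee immediately and under no circumstance should this exceed 24 hours". Clinically significant values are repeated (8.2.4). Under 7.1.2, "Temporary intervention discontinuation may be considered by the Investigator because of suspected AEs"; missing more than 2 consecutive doses then forces a permanent stop, and a restart requires the Investigator to judge the drug's responsibility unlikely and the selection criteria to be still met. Nor is the ALT case stopped at once, because it is rechecked first.

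A reader might also infer that a confirmed AST case stops only if someone chooses to stop it. That cannot be established, because the 10.6 flow chart is missing from the text under review. Its heading suggests ALT only but does not prove it.

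**Conclusion.** The difference in wording is real, and it opens a narrow gap within 7.1.1. A confirmed case with AST > 3, ALT ≤ 3 and bilirubin > 2 times ULN meets the protocol's own description of possible Hy's Law and no liver bullet in that section. Closing it is a cheap improvement of low severity.

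The practical size is small. Doses would continue only if both Investigator and Sponsor let a confirmed, reported case carry on, and only if 10.6 has no AST step. Such cases should be rare among 78 participants, though the documents give no rate. The 5-of-12 figure describes detection at the Week 12 sample and should not be read as a maximum. No endpoint, power or type I error is affected.

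**What to change.** At the next amendment, change the combined bullet in 7.1.1 to: *Serum ALT or AST > 3 × ULN and total bilirubin > 2 × ULN (see Section 10.6)*. Keep it subject to the recheck already in 7.1.1, and check that the 10.6 algorithm agrees. If ALT-only is intended, one sentence in 7.1.1 saying so is enough. The SAE examples in 10.3.2 are stated to be non-exhaustive and need no edit, and neither does the SAP.

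The text change is two words, plus any work that the 10.6 chart turns out to need. ALT, AST and bilirubin are already in the chemistry panel, so there are no new tests or visits. Ethics approval is required before an amendment takes effect (10.1.1), and the SAP lists five countries (Appendix 3). The documents show no further amendment planned, and this point alone should not trigger one. Meanwhile the Sponsor can use its existing right to request withdrawal for any confirmed AST-driven case.

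The downside is that a rare participant with a non-hepatic AST rise and raised bilirubin could be stopped. The recheck, and the creatine phosphokinase already in the same panel, limit that risk.
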